# 6.0 Study Procedures

# Weekly Casting Visits

Once study consent is obtained, the subject will undergo serial casting weekly by one of two board-certified Pediatric Orthopaedic surgeons using the Ponseti method to address their congenital idiopathic clubfoot. CCLS will be present to provide coping support and standardize the environment. This is routine care at our institution. During these castings, patient will wear pulse ox on hand, with mitten covering tool if needed, in order to measure heart rate and oxygen saturation. The CCLS, with assistance from a trained research assistant, will assess the subject's pain and temperament utilizing observational data and data collected from FLACC Scale. Observational assessment is also routine care, but the FLACC data, pulse ox and temperament questionnaire are new, being collected strictly for the study. Primary data will be obtained during casting of first foot and, in the case of bilateral clubfoot patients, a subgroup will be created utilizing data collected during casting of both feet.

Data collection during weekly castings will be obtained by a trained research assistant and will be event based, utilizing pulse ox and FLACC scale. Time points are as follows:

- Baseline before cast placement (patient placed on treatment table)
- Start of casting, after cast padding placed (1st cast if bilateral)
- End of casting (2nd cast if bilateral)

If the subject does not require tenotomy after the weekly casting, they will be withdrawn from the study.

# **Casting Visit 1 Week Prior to Tenotomy**

During the final casting visit prior to the subject's tenotomy, the subject's temperament will be assessed by the parents and CCLS by utilizing:

- An adapted temperament questionnaire for parents (research only)
- Assessment of subject over time by CCLS utilizing FLACC scale, O2, HR and chart notes.

On the day of or after the final casting visit, the participant will be randomized in equal proportion (1:1) to either the *control group* (receive L.M.X.4 cream with J-Tip saline injection) or the *intervention group* (placebo cream with J-Tip with 0.25mL of 1% Xylocaine

MPF). Researchers, physicians, nurses, CCLS, caregivers, and patients will be blinded to which group the patient is randomized. The only person who will remain unblinded is the research coordinator.

The Vanderbilt Investigational Drug Service will provide the 1% Xylocaine MPF, saline vials, L.M.X.4 and placebo creams. The Investigational Drug Service will store, blind and dispense the creams and the J-Tip vials.

# Tenotomy

On the day of the subject's tenotomy they will receive pain control based on their group assignment- L.M.X.4 cream (with J-Tip Saline) or J-Tip with 0.25mL of 1% Xylocaine MPF (with placebo cream). The treating physician will provide a Dimeglio score. The following procedures will take place:

- Baseline: FLACC and pulse ox data will be recorded as baby is positioned on treatment table
- Application of randomized topical cream (either L.M.X.4 or placebo cream) for 30 minutes timed.
- Peak FLACC and pulse ox data will be recorded within 5 seconds of application of LMX 4 or Placebo Cream
- Consent for tenotomy procedure will be obtained (routine care).
- Baseline #2: FLACC and pulse ox data will be recorded 30 minutes after cream application
- Parents will leave room (routine care).
- Patient stays with healthcare staff (Physician, nurse, CCLS, cast tech, trained research assistant)
- Cream will be removed from the subject's foot (routine care). Peak FLACC and Pulse Ox will be recorded within 5 seconds after cream removal.
- Baseline #3: FLACC and pulse ox data will be recorded 30 seconds after cream removal
- J-Tip injection with 1% Xylocaine MPF or saline. Peak FLACC scale measurements and pulse ox measurements will be recorded within 5 seconds of injection (1st foot if bilateral)
- Following J-Tip injection there will be a 3-minute break, baby will be calmed during this time.
- Baseline #4: FLACC scale measurements and pulse ox measurements 3 minutes after J-Tip injection
- Tenotomy will be performed
  - FLACC Scale data and Pulse Ox data will be measured during the following events:
    - Percutaneous incision for TAL (1st foot if bilateral)- Peak FLACC scale and Pulse Ox data will be recorded within 5 seconds of poke of scalpel
    - Start of casting, after cast padding placed (1st cast if bilateral)

• End of casting (2nd cast if bilateral)

Adverse local effects of the cream and/or J-Tip injection will be noted (skin redness, swelling, rash, etc). Procedural complications will be recorded (excessive bleeding, concern for neurovascular injury, etc).

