# Data Analysis

FLACC, heart rate, and oxygen saturation will be measured at 10 distinct time points (Table 1) during serial casting and following in-office TAL. Changes in FLACC score, heart rate, and oxygen saturation will be compared between treatment and control cohorts utilizing a two-way ANOVA with a Geisser-Greenhouse correction for matched time measures. A Sidak's multiple comparisons test will be utilized to assess differences between cohorts at each of the 10 time points assessed. To compare number of

complications between cohorts, data will be collected at 3-weeks post TAL and analyzed using a non-parametric Mann-Whitney test, given the ordinal nature of the data. Similar non-parametric analysis with correction for multiple comparisons between cohorts will be utilized to assess changes in responses to REDCap surveys. Statistical analysis will be conducted utilizing GraphPad Prism 8.3.0. Statistical significance will be p<0.05.

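### One 5-second peak rule covers FLACC and pulse oximetry: read literally it cannot show a fall in oxygen saturation, and it may show only part of a heart-rate response

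*Combined protocol and SAP*

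**What the plan says.** Section 6.0 (Tenotomy) takes readings at four stimuli, each with the word peak and a 5-second limit. At the incision: "Peak FLACC scale and Pulse Ox data will be recorded within 5 seconds of poke of scalpel". At cream removal: "Peak FLACC and Pulse Ox will be recorded within 5 seconds after cream removal". At the injection: "Peak FLACC scale measurements and pulse ox measurements will be recorded within 5 seconds of injection". Cream application has a rule of the same form.

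The baseline readings carry neither feature, for example "Baseline #4: FLACC scale measurements and pulse ox measurements 3 minutes after J-Tip injection". The readings at the start and end of casting also have no peak wording and no time limit.

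The device is described only under Weekly Casting Visits: "patient will wear pulse ox on hand, with mitten covering tool if needed, in order to measure heart rate and oxygen saturation". No model, averaging time or delay is given.

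Section 10.0 (Data Analysis) treats the three measures alike: "Changes in FLACC score, heart rate, and oxygen saturation will be compared between treatment and control cohorts utilizing a two-way ANOVA", followed by Sidak comparisons between arms at each of 10 time points. Both calculations under Power Analysis concern FLACC only.

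**The concern.** The three measures do not behave alike. A higher FLACC score or heart rate signals more distress, whereas a lower saturation does. A single word that ordinarily means the maximum therefore points the wrong way for saturation.

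The 5-second limit raises a second question. FLACC is scored from behaviour and can be read at once. A pulse oximeter typically displays a trailing average, and heart rate and saturation need time to change, so a value read within 5 seconds may still be partly made up of the period before the stimulus.

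The incision reading is the one taken at the procedural stimulus itself, and it is tested on its own. If the recording rule removes or dilutes a physiological difference there, a flat result says little about the two anaesthetics. This matters because the Aim 1 hypothesis is worded as equal or greater pain control, so a flat result could look like support.

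**Working it through.** The documents give no heart-rate or saturation effect, SD or sample size, so there is no figure of the plan's own to reproduce. The check is of the rule, then of its possible size.

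**1. Readings set side by side**

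| Event | Peak wording | Limit | Next scheduled reading or stimulus |
|---|---|---|---|
| Cream application | yes | 5 s | Baseline #2, at 30 min |
| Cream removal | yes | 5 s, stated as after the event | Baseline #3, at 30 s, then the injection |
| J-Tip injection | yes | 5 s | Baseline #4, at 3 min |
| Incision | yes | 5 s | start of casting, interval not stated |

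Peak appears at the events and not at the baselines. Only the cream-removal line says that the window follows the event. The others leave open whether it starts at the stimulus.

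**2. Saturation, literal reading**

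If saturation falls steadily from the stimulus, the maximum over 0 to 5 s is the value at time 0, so 0% of the fall is captured, whatever its depth. A displayed run of 99, 98, 96, 93 is recorded as 99; the minimum would be 93.

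**3. Either measure, if only the 5-second limit applies**

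All device and onset inputs are assumptions. Let A be the averaging time, L the delay and R the time over which a gradual change is completed.

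- *Immediate (step) change.* Share displayed at 5 s = min(1, (5 − L)/A).
  - L = 0: 100% for A = 2 or 4 s; 5/8 = 62% for 8 s; 5/12 = 42% for 12 s; 5/16 = 31% for 16 s.
  - L = 2 s: 100% for A = 2 s; 3/4 = 75% for 4 s; 3/8 = 38% for 8 s; 3/12 = 25% for 12 s; 3/16 = 19% for 16 s.
- *Gradual (linear) change, no delay.* Share = mean of s/R, held between 0 and 1, over the A seconds ending at 5 s.
  - A = 4, R = 5: the mean of s over 1 to 5 s is 3, and 3/5 = 60%.
  - A = 8, R = 5: (12.5/5)/8 = 31%.
  - A = 8, R = 15: (12.5/15)/8 = 10%.
  - A = 16, R = 30: (12.5/30)/16 = 3%.

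The range across both shapes is about 3% to 100%.

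**4. What a lost share would do to power (illustration)**

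Take an effect with 80% power at 47 per group (the group size in Power Analysis), a single two-sided test at 0.05, and unchanged noise. Power when a share f is captured is Φ(2.80 f − 1.96):

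- f = 0.75: Φ(0.14) = 56%
- f = 0.50: Φ(−0.56) = 29%
- f = 0.25: Φ(−1.26) = 10%

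**5. Saturation simulation (illustration under one assumed effect)**

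Inputs: 47 per arm; mean falls of 4 and 2 points (SD 2); baseline 98 (SD 1.2); averaging 4 or 8 s; onset 5 or 15 s. Two independent runs gave:

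| Value recorded | Difference between arms | Power |
|---|---|---|
| Highest in 5 s | 0.03 to 0.08 points | 4 to 6% |
| Lowest in 5 s | not tabulated | 7 to 82% |
| Lowest in 45 s | 1.8 to 1.9 points | 98 to 99% |

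The highest value performs at about the false-positive rate in every setting. The lowest value within 5 s depends heavily on the device and the onset. The 45 s row shows the direction only; a window that long would overrun Baseline #3 after cream removal.

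**The case against.** The strongest reply is that the text never says the highest saturation is taken. In the injection line the noun is repeated, so peak can attach to the FLACC measurements alone. It could also be meant loosely as the most extreme value. This stands, and the literal reading is therefore conditional.

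For heart rate, the maximum is the right direction. A reader might infer that the heart-rate value mostly reflects the time before the stimulus. The documents do not support that. An 8 s average read at 5 s has 5 of its 8 seconds after the stimulus. In the step model the pre-stimulus part dominates only when A exceeds 2 × (5 − L), that is, above 10 s with no delay or above 6 s with a 2 s delay. Neither figure can be checked against the protocol.

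The simulation assumes a desaturation, and a difference in it between arms, that no section predicts. It also ignores movement artefact, to which a lowest reading in a moving infant is exposed. So its power figures illustrate and do not estimate.

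Finally, FLACC carries the power calculation, the casting readings could show a later response, and nowhere does the plan say that a null heart-rate or saturation result would count as equality. All true. But the casting readings follow a new manipulation at an unstated interval after the incision, so they do not replace a usable event value.

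None of this supplies the missing definition. Under the literal reading the rule points the wrong way for saturation; under the others, what is recorded depends on the observer and on the device.

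**Conclusion.** The point stands as a defect in the recording rule for pulse oximetry at four event readings. Read literally, the saturation value captures none of a fall that begins at the stimulus. If peak governs FLACC only, between about 3% and 100% of a heart-rate or saturation response may be displayed, under assumed averaging times, delays and onset shapes. The event comparisons of saturation, and possibly of heart rate, may therefore be pulled toward no difference.

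A reader might go further and infer that two of the three outcomes are certainly biased to the null at the incision. That is not supported: the scope of the word is ambiguous, the maximum suits heart rate, and the device is undescribed. The FLACC comparison is not affected. This should be corrected, but it does not undermine the outcome on which the trial is sized.

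**What to change.** In Section 6.0 (Tenotomy), keep peak FLACC as it is and give pulse oximetry its own rule. For each event, record the highest heart rate and, separately, the lowest oxygen saturation over a fixed window that:

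- opens at the event;
- is longer than 5 seconds;
- is the same in both arms;
- ends before the next scheduled reading or stimulus, which for cream removal means before Baseline #3 at 30 seconds.

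Record the oximeter averaging setting. In Section 10.0 (Data Analysis), state that these are the values analysed at the event time points.

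The interim calculation already used FLACC observations from 39 patients, so some infants probably have event readings under the present rule. Report them with rule version as a factor, and do not read their peak saturation as evidence of no difference.

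The cost is a wording change in two sections and new case report form field definitions, using the oximeter already worn. There are three small downsides. Two rule versions will be mixed, which adds a factor to the planned two-way layout. The incision window will also cover the start of the next surgical step. And the extremes must be read from the display or from device memory over the window; the protocol does not say that the device stores data.

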#### Post-Tenotomy

#### **REDCap Text Message Survey Collection**

The subject's parents will receive a text or email message requesting they complete a REDCap survey 1, 7, 14, and 21 days after the tenotomy. They will be asked about the subject's pain level, irritability, doses of Tylenol administered, and any other problems that their child is having due to the procedure.

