#### Clinical Visit around 21 days post-tenotomy (This visit is part of subject's routine care)

The subject will be assessed for complications. The treating physician will provide a Dimeglio score. A parental survey will be administered regarding quality of care, postoperative care, and perception of subject's pain level.

REDCap Survey questions to be sent to parents post TAL						
REDCap Survey	1. On a scale of 1-5, with 1 being no pain and 5 being extreme					
Postop Day 1	pain, how much pain is your child having today due to the					
	procedure?					
	2. On a scale of 1 to 5, with 1 being no irritability and 5 being					
	extreme irritability, how irritable is your child today due to the procedure?					
	3. How many doses of Tylenol (acetaminophen) has your child					
	been given today due to pain from the procedure?					
	4. If applicable, please list any other problems that your child is					
	having today, due to the procedure.					
REDCap Survey	1. On a scale of 1-5, with 1 being no pain and 5 being extreme					
Postop Day 7, 14	pain, how much pain has your child had over the last week due to					
& 21	the procedure?					
	2. On a scale of 1 to 5, with 1 being no irritability and 5 being					
	extreme irritability, how irritable has your child been over the last					
	week due to the procedure?					
	3. On average, how many doses of Tylenol (acetaminophen) per					
	day have been given to your child over the last week due to pain					
	experienced from procedure?					
	4. If applicable, please list any other problems your child has had					
	over the last week, due to the procedure.					

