#### 8.0 Reporting of Adverse Events or Unanticipated Problems involving Risk to Participants or Others

The relationship of each adverse event to treatment rendered as judged by the investigator will be recorded on the Adverse Event Report Form. Due to the nature of the procedure involved in this study, certain adverse events may be considered normal sequalae associated with the procedure and will only be recorded if additional treatment is required or considered to be clinically significant. See specific indications for expected adverse events/complications due to nature of diagnosis.

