#### **Definitions**

An AE can be any unfavorable and unintended sign, symptom, or disease temporally associated with the use of an investigational product, whether or not related to the investigational product.

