#### **Reporting Adverse Events**

Any adverse event (clinical sign, symptom, or disease) temporally associated with the study treatment shall be documented in the adverse event (AE) CRF, except those events that are considered to be normal sequalae to the surgical procedure. All AE's meeting the above noted criteria are to be reported by the subject or observed by the Principal Investigator will be individually listed. The description of the event (confirmed diagnosis, if available), date of onset, date of resolution, action taken, severity and relationship to study treatment, and follow-up procedures will be reported.

The adverse event will be recorded in standard medical terminology. Additionally, the Principal Investigator will evaluate all adverse events as follows:

Action taken: whether or not the adverse event caused the subject to discontinue the study

Severity, to be assessed based on the table below:

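### The parent survey asks about other problems only if the parent blames the procedure, so later events with no perceived link are not solicited before the day-21 visit

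*Combined protocol and SAP*

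**What the plan says.** Section 6.0 (REDCap Text Message Survey Collection) has parents "complete a REDCap survey 1, 7, 14, and 21 days after the tenotomy". The open question covers other problems only under a causal condition: "and any other problems that their child is having due to the procedure".

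The table of survey questions shows that this condition is in the instrument and not only in the summary. The day-1 item begins "4. If applicable, please list any other problems that your child is" and the item for days 7, 14 and 21 begins "4. If applicable, please list any other problems your child has had". Both end by restricting the answer to problems caused by the procedure. The pain, irritability and Tylenol items carry the same restriction; the day-1 pain item, for example, asks about pain the child is "having today due to the procedure".

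Section 8.0 takes a different approach. Its Definitions paragraph counts any unfavourable event temporally associated with the product, "whether or not related to the investigational product". Under Reporting Adverse Events, any event "temporally associated with the study treatment shall be documented in the adverse event (AE) CRF", apart from normal sequelae of the surgery. Causation is the investigator's task: "The relationship of each adverse event to treatment rendered as judged by the investigator will be recorded".

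**The concern.** The definition in Section 8.0 separates two steps: first record what happened, then have the investigator grade its relationship to treatment. Survey item 4 reverses them. The parent must settle causation before anything is written down, and whatever the parent filters out cannot be graded.

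Parents are not well placed to make that judgement. Under Tenotomy in Section 6.0 they are present while the cream is on, but they leave before it is removed and before the injection and incision. A parent might not connect a systemic or delayed sign with a procedure on the foot.

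Aim 2 is at stake. It compares adverse event rates and hypothesises no increase with J-Tip. Incomplete capture in both arms makes that result easier to reach.

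**Working it through.** The plan states no figure on this point, so the check is of the text: which scheduled contacts could bring an event to light, and on what terms.

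| Contact | What is sought | Needs the parent to attribute cause? |
|---|---|---|
| Tenotomy day (6.0, Tenotomy) | Local effects of cream and injection; procedural complications; heart rate and oxygen saturation at set steps | No; staff observe |
| Days 1, 7, 14, 21 (REDCap surveys) | Pain, irritability, Tylenol doses, other problems | Yes, in all four items |
| Visit around day 21 (6.0) | Assessment for complications | No |
| Parental survey at that visit | Quality of care, postoperative care, perceived pain | No question on other problems |
| Any time (8.0, Reporting Adverse Events) | Events reported by the subject or observed by the investigator | No, but nobody asks |

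The adverse event review row in the Schedule of Events has two marks. It is detached from its column headings in the text available; I take the marks to be tenotomy day and day 21, which fits the rest of the plan.

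1. *Coverage in time.* The surveys on days 7, 14 and 21 each look back one week, so the three weeks are covered. The gap is therefore one of attribution, not of timing.
2. *Coverage by cause.* No item between the two ends asks about problems whatever their cause, and none names the cream or the injection.
3. *Direction of effect.* For arm *k*, let *a* be the proportion of infants whose event is found by a route that item 4 does not affect. Let *b* be the proportion whose only event would come to light through item 4, and *c* the share of those that parents attribute to the procedure. The recorded rate is *a* + *cb*; under an all-cause question it would be *a* + *b*. With the same *c* in both arms, the between-arm difference (J-Tip minus L.M.X.4) falls short by (1 − *c*)(*b*_J − *b*_L). This is zero if parents attribute everything (*c* = 1) or if such events are equally common in both arms. It is never larger in size than *b*_J − *b*_L. If J-Tip has the excess both overall and among these events, the recorded difference moves toward zero.
4. *Size.* The documents give none of *a*, *b* or *c*, so no number follows.

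**The case against.** Much of the case on the other side stands.

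- A reader might infer that the survey names the tenotomy as the cause and so excludes the anaesthetic. It does not: it refers to the procedure without defining it. Cream, injection and tenotomy are steps of one visit, and many parents may include a reaction to any of them. The gap is limited to problems that a parent links to none of these.
- A reader might infer that anaesthetic reactions go unrecorded. Section 7.0 lists rash, redness, irritation, swelling and heart-rhythm problems. Staff note local effects on the day, and heart rate is recorded around cream, injection and incision. A long-leg cast then covers the site for about three weeks under the method described in Section 1.0, so most local reactions would be out of the parent's sight whatever the wording. What remains is later or systemic events.
- A reader might infer that the survey breaches Section 8.0. The plan does not name the survey as its adverse event collection tool, and events may still be reported spontaneously or found at the day-21 assessment. The mismatch is in what is solicited, not in what may be recorded.
- A reader might try to express the loss as reduced power for Aim 2. The documents support no such figure. They give no event rates and no share of events that depend on item 4. Section 10.0 takes complications from data collected at three weeks, analyses survey responses separately, and does not say that item 4 feeds the complication count.
- Caregivers are blinded, so the expected effect is lost sensitivity, not a bias favouring one arm.

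These points limit the size of the problem. They do not supply an all-cause question between tenotomy day and day 21.

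**Conclusion.** The point holds in a limited form. Item 4 makes the parent's view of cause a condition of reporting, although Section 8.0 defines events without regard to cause and gives that judgement to the investigator. Later or systemic events that a parent does not link to the procedure are not solicited until the day-21 visit, and before then reach the trial only if someone volunteers them.

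The size is unknown and probably modest. The consequence is lower sensitivity of safety capture and a lean toward no difference in Aim 2, to the extent that parent-reported events count there. This rests on two assumptions: that parents in the two arms attribute events similarly, which blinding makes likely but does not guarantee if the arms produce different kinds of event; and that spontaneous report and day-21 recall do not recover everything. The FLACC comparison is unaffected. The change is worth making because it is cheap, not because the present wording invalidates the trial.

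**What to change.** 1. Reword item 4 to ask for any problems since the procedure (day 1) or over the last week (days 7, 14 and 21), whatever the parent thinks the cause. Keep the causal wording in the pain, irritability and Tylenol items, where attribution is intended.
2. Enter answers that meet the Section 8.0 recording rule on the adverse event form when received, with relationship graded by the blinded investigator on the existing four-level scale.
3. State in Section 10.0 how these events are used: all-cause events reported by arm descriptively, with the Aim 2 comparison also given for events graded likely or definite. Without that second comparison the rewording would weaken Aim 2. An independent background illness rate *g* turns an event rate *p* into *p* + *g*(1 − *p*), so the between-arm difference shrinks by the factor 1 − *g*.

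The cost is a one-item change in REDCap, a minor amendment, and more unrelated infant illness to list and grade. Item wording will differ between earlier and later infants, equally in both arms.
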